Clinical Drug Supplies		
IRT Drug Vial Assignment	X	
Administer Study Treatment	X	Note: Within 72 hours from vial assignment, the participant must receive the dose of study medication.

Table 2-4: Follow-up Assessments (CA209800)

Procedure	Follow Up, ^a Visits X1 and X2	Survival, ^b Follow-up Y Visits	Notes
Safety Assessments			
Targeted Physical Examination	X		To assess for potential late emergent study treatment related issues
Adverse Event Assessments	X	X	
Laboratory Tests	X		On site/local CBC w/differential, LFTs, BUN, creatinine, amylase, lipase and TSH (+ reflex Free T4 and Free T3) for X1, repeat at X2 if study treatment related toxicity persists.
Pregnancy Test (WOCBP Only)	X		Serum or urine
Review of Concomitant Medications	X		
Pharmacokinetic Samples and Immunogenicity Assessments			
PK Samples	X		Refer to Table 9.5-1
Immunogenicity blood sample	X		Refer to Table 9.5-1
Survival Status			
Participant Status	X	X	Every 3 months, Survival Follow up Visits may be accomplished by visit or phone contact, to include subsequent anti-cancer therapy
Efficacy Assessments			
Tumor Assessments	See Notes		
Only for participants without progression on study therapy. SUBSEQUENT tumor assessments should continue to occur every 8 weeks (\pm 1 week) thereafter for the first 12 months, then every 12 weeks (\pm 2 weeks) until disease progression or treatment discontinuation, whichever occurs later.
 
Contrast enhanced CT Chest, CT (or MRI with and without contrast) abdomen, pelvis and all known sites of disease. Use same imaging method as was used at screening/baseline.
 
Participants with a history of brain metastasis should have surveillance MRI

Table 2-4: Follow-up Assessments (CA209800)

Procedure	Follow Up, ^a Visits X1 and X2	Survival, ^b Follow-up Y Visits	Notes
			Brain without and with gadolinium approximately every 12 weeks, or sooner if clinically indicated (until disease progression or treatment discontinuation, whichever occurs later).
Outcomes Research Assessments			
FACT-G and FKSI-19	X		Collection done at X1 and X2 only
EQ-5D-3L	X	X	Collection done during X1 and X2. Survival follow-up every 3 months for the first year and 6 months thereafter
Health Care Utilization	X		Collection done at X1 and X2 only
████████████████████			
██████████	█	█	██

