7.4.3 Dose Discontinuation

The assessment for discontinuation of nivolumab should be made separately from the assessment made for discontinuation of ipilimumab. Although there is overlap among the discontinuation criteria, if discontinuation criteria are met for ipilimumab but not for nivolumab, treatment with nivolumab may continue if ipilimumab is discontinued. In this instance, the patient would be considered off part 1 of the study and must have a 6 weeks interval before moving on to part 2 of the study (nivolumab monotherapy).

If a participant in any of the nivolumab/ipilimumab combination arms meets criteria for discontinuation and investigator is unable to determine whether the event is related to both or one study drug, the participant should discontinue both nivolumab and ipilimumab and be taken off the treatment phase of the study.

Study treatment should be permanently discontinued for the following:

- Any Grade 2 drug-related uveitis, eye pain or blurred vision that does not respond to topical therapy and does not improve to Grade 1 severity within the re-treatment period OR requires systemic treatment
- Any Grade 3 non-skin, drug-related adverse event lasting $>$ 7 days, or recurs with the following exceptions for laboratory abnormalities, diarrhea, colitis, neurologic toxicity, drug-related

uveitis, pneumonitis, bronchospasm, myositis, myocarditis, rhabdomyolysis, hypersensitivity reactions, infusion reactions, and endocrinopathies:

- Grade 3 drug-related, diarrhea, colitis, neurologic toxicity, uveitis, pneumonitis, bronchospasm, myositis, myocarditis, rhabdomyolysis, hypersensitivity reaction, or infusion reaction of any duration requires discontinuation
- Grade 3 drug-related endocrinopathies, adequately controlled with only physiologic hormone replacement do not require discontinuation. Adrenal insufficiency requires discontinuation regardless of control with hormone replacement.
- Grade 3 drug-related laboratory abnormalities do not require treatment discontinuation except:
 - ◆ Grade 3 drug-related thrombocytopenia > 7 days or associated with bleeding requires discontinuation
 - ◆ Any drug-related liver function test (LFT) abnormality that meets the following criteria requires discontinuation:
 - Grade \geq 3 drug-related AST, ALT or Total Bilirubin requires discontinuation*
 - Concurrent AST or ALT > 3 x ULN and total bilirubin > 2x ULN

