- For future infusions, the following prophylactic premedications are recommended: diphenhydramine 50 mg (or equivalent) and/or acetaminophen/paracetamol 325 to 1000 mg should be administered at least 30 minutes before infusions. If necessary, corticosteroids (up to 25 mg of hydrocortisone or equivalent) may be used

For Grade 3 or 4 symptoms: (severe reaction, Grade 3: prolonged [ie, not rapidly responsive to symptomatic medication and/or brief interruption of infusion]; recurrence of symptoms following initial improvement; hospitalization indicated for other clinical sequelae (eg, renal impairment, pulmonary infiltrates). Grade 4: Life-threatening; pressor or ventilatory support indicated):

- Immediately discontinue infusion of study treatment. Begin an IV infusion of normal saline and treat the participant as follows: Recommend bronchodilators, epinephrine 0.2 to 1 mg of a 1:1000 solution for subcutaneous administration or 0.1 to 0.25 mg of a 1:10,000 solution injected slowly for IV administration, and/or diphenhydramine 50 mg IV with methylprednisolone 100 mg IV (or equivalent), as needed. Participant should be monitored until the Investigator is comfortable that the symptoms will not recur. Study treatment will be permanently discontinued. Investigators should follow their institutional guidelines for the treatment of anaphylaxis. Remain at bedside and monitor participant until recovery of the symptoms

In case of late-occurring hypersensitivity symptoms (eg, appearance of a localized or generalized pruritus within 1 week after treatment), symptomatic treatment may be given (eg, oral antihistamine or corticosteroids).

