9.5 Pharmacokinetic

Samples for PK and immunogenicity assessments will be collected for all participants receiving nivolumab and ipilimumab as described in [Table 9.5-1](#). All timepoints are relative to the start of study treatment administration. All on-treatment timepoints are intended to align with days on which study treatment is administered. If it is known that a dose is going to be delayed, then the predose sample should be collected just prior to the delayed dose. However, if a predose sample is collected but the dose is subsequently delayed, an additional predose sample should not be collected. Further details of sample collection, processing, and shipment will be provided in the laboratory procedures manual.

Blood samples should be drawn from a site other than the infusion site (ie, contralateral arm) on days of infusion. All samples collected pre-dose should be taken just prior to the administration from the contralateral arm (ie, the arm not used for the infusion). If the infusion was interrupted, the interruption details will also be documented on the CRF. Blood samples will be processed to collect serum and stored preferably at -70°C (samples may be stored at -20°C up to 2 months). Further details of pharmacokinetic sample collection and processing will be provided to the site in the lab manual.

Serum samples will be analyzed for drug (nivolumab and ipilimumab) and ADA (anti-nivolumab and anti- ipilimumab antibodies) by validated immunoassays. Samples with a positive ADA response may also be analyzed for neutralizing ADA response to nivolumab and/or ipilimumab.

In addition, selected serum samples may be analyzed by an exploratory method that measures nivolumab and ipilimumab, or detect anti-drug antibodies for technology exploration purposes; exploratory results will not be reported. The corresponding serum samples designated for either PK, immunogenicity or biomarker assessments may also be used for any of those analyses, if required (eg, insufficient sample volume to complete testing or to follow up on suspected immunogenicity related AE).

Table 9.5-1: Pharmacokinetic and Immunogenicity Sample Collections (CA209800 Arms A and B)							

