Part^a	Study Day^b (1 Cycle = 3 weeks for Part 1 1 Cycle = 4 Weeks for Part 2)	Time (Event)	Time (Relative to Start of Infusion) Hours:Min	Pharmacokinetic Blood Sample for Nivolumab	Immunogenicity Blood Sample for Nivolumab	Pharmacokinetic Blood Sample for Ipilimumab	Immunogenic Blood Sample for Ipilimumab
1	C1D1	(Predose) ^c	00:00	X	X	X	X
1	C1D1	(EOI-nivo) ^d	00:60	X			
1	C1D1	(EOI-ipi) ^d	00:60 or 00:30			X	
1	C2D1	(Predose) ^c	00:00	X	X	X	X
1	C2D1	(EOI-nivo) ^d	00:60	X			
1	C2D1	(EOI-ipi) ^d	00:60 or 00:30			X	
1	C4D1	(Predose) ^c	00:00	X	X	X	X
1	C4D1	(EOI-nivo) ^d	00:60	X			
1	C4D1	(EOI-ipi) ^d	00:60 or 00:30			X	
2	C5D1	(predose)	00:00	X	X	X	X
2	CXD1: Every 16 weeks starting with C5D1 (ie, C9D1, C13D1, etc.)	(Predose)	00:00	X	X		
	First 2 Follow-up Visits (Approximately 30 days and up to ~ 100 Days from the Discontinuation of Study treatment)	NA		X	X		

^a Part 1 indicates first 12 weeks (or 4 cycles) of combination treatment (nivolumab + ipilimumab). Part 2 indicates nivolumab monotherapy period starting from Week 16 (or Cycle 5).

^b If a participant discontinues study treatment during the sampling period, they will move to sampling at the follow-up visits.

^c Predose: All predose samples for nivolumab and ipilimumab should be taken prior to the start of nivolumab or FRC infusion.

^d EOI-nivo and EOI-ipi PK samples: End of Infusion PK samples for nivolumab and ipilimumab, respectively. **For sequential dosing, EOI samples for nivolumab and ipilimumab should be collected immediately (preferably within 2 - 5 minutes) prior to the end of the 60 minute nivolumab infusion and 30 minutes ipilimumab infusion, respectively. For the FRC dosing, EOI samples for nivolumab and ipilimumab should be collected immediately**

(preferably within 2 - 5 minutes) prior to the end of the 60 min FRC co-infusion. If the end of any infusion is delayed, the collection of the EOI samples should be delayed accordingly.

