### 6.3 Populations for Analyses

Since the primary objective will be addressed by a safety endpoint, the primary endpoint analysis will be based on all treated subjects. For consistency, the secondary endpoints will use the same analysis population as the primary endpoint (ie, all treated subjects).

Population	Description
All Enrolled Subjects	All subjects who signed an informed consent form and were registered into the IRT.
All Randomized Subjects	All subjects who were randomized to any treatment group. This is the primary dataset for efficacy listings.
All Treated Subjects	All subjects who received at least one dose of any study medication. This is the primary dataset for analysis of study conduct, study population, efficacy (including secondary endpoints), exposure, and safety (including primary endpoint).
All Treated Subjects in Part 2	All subjects who received at least one dose of study medication in the open-label nivolumab flat dose maintenance phase (Part 2).
Response-Evaluable Subjects	All treated subjects with measurable disease at a baseline tumor assessment and at least one on-treatment tumor assessment.
Pharmacokinetic Subjects	All treated subjects with available serum time-concentration data.
Immunogenicity Subjects	
All treated subjects with available ADA data.
 
 
- Nivolumab ADA evaluable subjects: all treated subjects with baseline and at least 1 postbaseline nivolumab immunogenicity assessment.
 
- Ipilimumab ADA evaluable subjects: all treated subjects with baseline and at least 1 postbaseline ipilimumab immunogenicity assessment.
 

[REDACTED]	
[REDACTED]
 
 
■ [REDACTED]
 
■ [REDACTED]
 
■ [REDACTED]
 

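### A participant who stops all study treatment after the first Part 1 dose has no scheduled post-baseline ipilimumab ADA sample, because the follow-up visits sample for nivolumab only

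*Protocol*

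**What the plan says.** Protocol Table 9.5-1 schedules ipilimumab immunogenicity samples before dosing at Cycles 1, 2, 4 and 5. The end-of-infusion ipilimumab samples at Cycles 1, 2 and 4 are for PK only. For early stoppers, footnote b says: "If a participant discontinues study treatment during the sampling period, they will move to sampling at the follow-up visits".

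The row for those visits is labelled "First 2 Follow-up Visits (Approximately 30 days and up to ~ 100 Days from the Discontinuation of Study treatment". It carries marks for nivolumab PK and nivolumab immunogenicity, and none for ipilimumab. The follow-up schedule in Table 2-4 adds nothing of its own; for both PK and immunogenicity it says "Refer to Table 9.5-1".

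SAP 6.3 defines two nested sets. The broad immunogenicity population is "All treated subjects with available ADA data". The narrower one is "Ipilimumab ADA evaluable subjects: all treated subjects with baseline and at least 1 postbaseline ipilimumab immunogenicity assessment", with a parallel definition for nivolumab.

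Two places in the Protocol link stopping to infusion reactions. Section 7.4.3 says that a Grade 3 drug-related "hypersensitivity reaction, or infusion reaction of any duration requires discontinuation". Section 7.4.5, for Grade 3 or 4 reactions, says "Study treatment will be permanently discontinued".

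Section 9.5 also has a reuse clause: "The corresponding serum samples designated for either PK, immunogenicity or biomarker assessments may also be used for any of those analyses". It applies where needed, and one of its two examples is the follow-up of an adverse event suspected to be related to immunogenicity.

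**The concern.** The trial compares a new co-formulated product with sequential infusion on anaphylactic-type events. Anti-drug antibody data on both components are a natural supporting measure if the arms differ. As scheduled, the two components are treated unequally. A participant who leaves treatment after one dose can still contribute a nivolumab ADA result but not an ipilimumab one.

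Some reasons for leaving after one dose are related to the events under study, above all a severe infusion reaction. The missing ipilimumab results are therefore not missing at random with respect to safety. If early stopping differs between arms, the gap could differ too. At stake is the completeness of the ipilimumab immunogenicity summary, not the primary comparison.

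**Working it through.** The plan states no figure on this point, so there is none to reproduce. The check counts scheduled samples and then applies the SAP definition.

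**Inputs**
- Post-baseline predose ADA samples in Part 1: Cycles 2 and 4, for both drugs (Table 9.5-1).
- Follow-up ADA samples: 2 for nivolumab, 0 for ipilimumab (Table 9.5-1, follow-up row).
- Evaluable: a baseline and at least one post-baseline assessment (SAP 6.3).
- Treated participants: 50 per arm (Protocol 10.1).

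**Step 1. Scheduled post-baseline ADA samples when all treatment stops in Part 1**

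Count = predose samples at Cycles 2 and 4 reached before stopping + follow-up samples, with both follow-up visits attended.

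| Doses received | Ipilimumab | Nivolumab | Ipilimumab ADA evaluable? |
|---|---|---|---|
| 1 | 0 + 0 = 0 | 0 + 2 = 2 | No |
| 2 | 1 + 0 = 1 | 1 + 2 = 3 | Yes |
| 3 | 1 + 0 = 1 | 1 + 2 = 3 | Yes |
| 4 | 2 + 0 = 2 | 2 + 2 = 4 | Yes |

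Only a stop after dose 1 leaves no ipilimumab sample. If the follow-up row also carried ipilimumab, that count would rise from 0 to as many as 2, equal to nivolumab.

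**Step 2. Who is outside the gap**
- A participant who stops ipilimumab alone goes to Part 2 after a 6-week interval (Protocol 7.4.3) and has the Cycle 5 predose ipilimumab ADA sample.
- A participant whose Cycle 2 predose blood was drawn before the decision to stop has a post-baseline sample.
- An Arm B participant stopped during the first nivolumab infusion never received ipilimumab, so no treatment-emergent result is lost.

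**Step 3. Possible size**

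The documents give no rate of stopping all treatment after dose 1. Assume 2% to 10%:
- 0.02 × 50 = 1 per arm
- 0.10 × 50 = 5 per arm

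To illustrate, suppose 2 participants in an arm test positive:
- 1 missing: observed 2/49 = 4.1%; possible range over all 50 is 2/50 = 4% to 3/50 = 6%.
- 5 missing: observed 2/45 = 4.4%; possible range is 2/50 = 4% to 7/50 = 14%.

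**Step 4. The share due to infusion reactions**

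For an earlier study of the combination, Protocol 7.1.1 cites hypersensitivity or infusion reactions in 3.2%, none of Grade 3 or 4. Applied here, 0.032 × 50 = 1.6 per arm, at any grade and any dose. Stops forced by a severe reaction at the first dose should be fewer than that, and may be none. That study did not use the fixed-ratio product, so the rate is only a guide.

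**Step 5. Timing of a follow-up sample**

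Table 2-4 normally places X1 at 30 ± 7 days after the last dose, that is 23 to 37 days. The plan already tests ipilimumab ADA about 21 days after a dose (Cycle 2 predose) and 42 days after a dose (Cycle 5 predose). X1 falls between these. X2 comes 84 days after X1 and is well outside that span.

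**The case against.** The strongest reply is that the reuse clause in Section 9.5 already covers the case that matters. Serum is drawn at both follow-up visits, and a severe reaction at the first dose fits the clause's own example. This stands in part: such a participant lacks a scheduled result, not necessarily any result. But the clause permits the test without requiring it, and does not name ipilimumab ADA at follow-up. Used only for suspected cases, it would test reactors and skip other early stoppers, which is a selection of its own.

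A reader might also infer that the plan discards its most informative participants. The documents do not support that. Antibody that develops after a first-infusion reaction cannot have caused it, and the sample that precedes the reaction, Cycle 1 predose, is collected.

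Nor do they support a reading that missing results are concentrated among participants with the primary-endpoint event. That endpoint counts broad-scope terms such as cough, rash and pruritus at any grade, most of which need not end treatment. Section 7.4.5 deals with Grade 1 and 2 reactions without requiring permanent discontinuation.

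Finally, immunogenicity is not among the six listed secondary endpoints, and SAP 7.6.16 only refers to a Core Safety SAP that is not part of these documents. No visible passage plans an analysis of ipilimumab ADA against anaphylactic-type events. That objection stands and limits the importance of the point.

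**Conclusion.** The gap is real but of modest importance. It applies to participants who stop all study treatment after dose 1, and it costs them membership of the ipilimumab ADA evaluable set only. They remain in All Treated, in the broad immunogenicity population if they have any ADA data and, if sampled at follow-up with a baseline result, in the nivolumab ADA evaluable set. Stops after dose 2 or 3 leave one ipilimumab sample and do not cost evaluability. The primary endpoint, the Grade 3 to 5 AE rates, ORR and PFS do not depend on these samples.

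The 1 to 5 per arm rests wholly on the assumed 2% to 10%, and the part due to severe first-dose reactions is probably very small. The point is still worth acting on. Part of the loss is related to safety outcome, it follows directly from the schedule as written, and it costs little to remove. Samples that are neither taken nor tested in time may not be recoverable.

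**What to change.** In the follow-up row of Table 9.5-1, mark ipilimumab immunogenicity, with ipilimumab PK to help interpret it, at the first two follow-up visits. Restrict the mark by footnote to participants who received ipilimumab and stopped all study treatment during Part 1. If two samples are thought excessive, X1 alone would make a participant who stopped after dose 1 evaluable, provided the baseline sample exists. Table 2-4 needs no edit, since it points to Table 9.5-1.

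The serum would come from the blood draw already scheduled at those visits for nivolumab, so no extra visit or draw is needed. The laboratory manual should confirm that the volume is enough. The cost is two table cells, a footnote and a few extra assays. The one drawback is that these samples fall later after dosing than the Cycle 2 predose sample, so the report should state the time since last dose for any result obtained this way.

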7.1 Treatments Administered

7.1.1 Part 1 Study Treatment Administration

In Part 1 of the study there will be two treatment arms:

Arm A BMS-986237 (nivolumab 3 mg/kg/ipilimumab 1 mg/kg as a single infusion) will be administered as one 60-minute infusion on Day 1 of each treatment cycle every 3 weeks for 4 doses or until progression, unacceptable toxicity, withdrawal of consent, or the study ends, whichever occurs first.

Arm B nivolumab and ipilimumab will be administered sequentially, as two separate infusions, one 60 minute nivolumab infusion and one 30-minute ipilimumab infusion with a 30-minute break between each infusion. Nivolumab is to be administered first. Participants should receive nivolumab at a dose of 3 mg/kg as a 60-minute IV infusion, on Day 1 of each treatment cycle every 3 weeks for 4 doses or until progression, unacceptable toxicity, withdrawal of consent, or the study ends, whichever occurs first. Participants should begin study treatment within 3 calendar days of randomization.

The second infusion will always be ipilimumab, and the time in between infusions is expected to be approximately 30 minutes but may be more or less depending on the situation. Participants should receive ipilimumab at a dose of 1 mg/kg as a 30-minute IV infusion, on Day 1 of each treatment cycle every 3 weeks for 4 doses or until progression, unacceptable toxicity, withdrawal of consent, or the study ends, whichever occurs first.

Dosing calculations should be based on the body weight assessed at baseline. It is not necessary to re-calculate subsequent doses if the participant weight is within 10% of the weight used to calculate the previous dose. All doses should be rounded up or to the nearest milligram per institutional standard.

The nivolumab infusion must be promptly followed by a saline flush to clear the line of nivolumab before starting the next infusion.

Both agents given as single agents are uncommonly associated with infusion reactions, incidence less than 1% for ipilimumab (Yervoy® FDA Label) and for nivolumab 3% (Opdivo® FDA Label). In the CA209069 study, hypersensitivity/infusion reactions were listed as 3.2% for the combination and 2.2% for ipilimumab. No Grade 3 or Grade 4 hypersensitivity/infusion reactions were observed in either the combination or single agent ipilimumab treatment groups.²⁸

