Nivolumab injection is to be administered as a ~ 60-minute IV infusion through a 0.2-micron to 1.2-micron pore size, low-protein binding (polyethersulfone membrane) in-line filter at the

protocol specified doses and infusion times. It is not to be administered as an IV push or bolus injection. Nivolumab injection can be infused undiluted (10 mg/mL) or diluted with 0.9% Sodium Chloride Injection, USP or 5% Dextrose Injection, USP to protein concentrations as low as 0.35 mg/mL. During drug product preparation and handling, vigorous mixing or shaking is to be avoided. Instructions for dilution and infusion of nivolumab injection are provided in the clinical protocol, pharmacy binder, pharmacy manual, or pharmacy reference sheet. Care must be taken to assure sterility of the prepared solution as the product does not contain any antimicrobial preservative or bacteriostatic agent. Nivolumab infusions are compatible with polyvinyl chloride (PVC) or polyolefin containers and infusion sets, and glass bottles. Vials of nivolumab injection must be stored at 2°C to 8°C (36°F to 46°F) and protected from light and freezing.

Ipilimumab injection can be used for IV administration without dilution after transferring to a PVC, non-PVC/non-DEHP or glass container and is stable for 24 hours at 2° - 8°C or room temperature/room light (RT/RL). For ipilimumab storage instructions, refer to ipilimumab IB and/or pharmacy reference sheets.

Separate infusion bags and filters should be used when administering nivolumab and ipilimumab on the same day.

Ipilimumab is to be administered as a ~30 minute IV infusion, using a volumetric pump with a 0.2 to 1.2 micron in-line filter at the protocol-specified dose. The drug can be diluted with 0.9% normal saline or 5% Dextrose Injection to concentrations between 1 mg/mL and 4 mg/mL. It is not to be administered as an IV push or bolus injections. Care must be taken to assure sterility of the prepared solutions, since the drug product does not contain any antimicrobial preservatives or bacteriostatic agents. At the end of the infusion, flush the line with a sufficient quantity of normal saline or 5% dextrose solution.

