7.4.5 Treatment of Related Infusion Reactions

Since study treatment contains only human immunoglobulin protein sequences, it is unlikely to be immunogenic and induce infusion or hypersensitivity reactions. However, if such a reaction were to occur, it might manifest with fever, chills, rigors, headache, rash, pruritus, arthralgias, hypotension, hypertension, bronchospasm, or other allergic-like reactions. All Grade 3 or 4 infusion reactions should be reported within 24 hours to the study medical monitor and reported as an SAE if it meets the criteria. Infusion reactions should be graded according to NCI CTCAE (Version 4.0) guidelines.

Treatment recommendations are provided below and may be modified based on local treatment standards and guidelines, as appropriate:

For Grade 1 symptoms: (mild reaction; infusion interruption not indicated; intervention not indicated):

- Remain at bedside and monitor participant until recovery from symptoms. The following prophylactic premedications are recommended for future infusions: diphenhydramine 50 mg (or equivalent) and/or acetaminophen/paracetamol 325 to 1000 mg at least 30 minutes before additional administrations.

For Grade 2 symptoms: (moderate reaction required therapy or infusion interruption but responds promptly to symptomatic treatment [(eg, antihistamines, non-steroidal anti-inflammatory drugs, narcotics, corticosteroids, bronchodilators, IV fluids); prophylactic medications indicated for ≤ 24 hours]):

- Stop the study treatment infusion, begin an IV infusion of normal saline, and treat the participant with diphenhydramine 50 mg IV (or equivalent) and/or acetaminophen/paracetamol 325 to 1000 mg; remain at bedside and monitor participant until

resolution of symptoms. Corticosteroid and/or bronchodilator therapy may also be administered as appropriate. If the infusion is interrupted, then restart the infusion at 50% of the original infusion rate when symptoms resolve; if no further complications ensue after 30 minutes, the rate may be increased to 100% of the original infusion rate (**for Arm B subjects**) or to 50% of the original infusion rate (**for Arm A subjects**) until completion of the infusion. Monitor participant closely. If symptoms recur, then no further study treatment will be administered at that visit.

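### Ipilimumab end-of-infusion samples are drawn the same few minutes early from a 60-minute and a 30-minute infusion, so the fixed ratio combination (FRC) reads about 4% (2 minutes) to 10% (5 minutes) too high at Cycle 1

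*Protocol*

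**What the plan says.** Footnote d of Table 9.5-1 (Protocol 9.5) governs the EOI samples at Cycles 1, 2 and 4. In the sequential arm they are to be "collected immediately (preferably within 2 - 5 minutes) prior to the end of the 60 minute nivolumab infusion and 30 minutes ipilimumab infusion". In the FRC arm the same preferred 2-5 minute lead applies, this time "prior to the end of the 60 min FRC co-infusion". The nominal times in the table body are 60 or 30 minutes from the start of infusion, which is the planned end, so table and footnote do not quite agree. If an infusion ends late, the footnote moves the sample accordingly.

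Protocol 7.1.1 gives Arm A one 60-minute infusion containing ipilimumab 1 mg/kg. Arm B receives "one 60 minute nivolumab infusion and one 30-minute ipilimumab infusion with a 30-minute break between each infusion", with ipilimumab also at 1 mg/kg.

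Protocol 10.3.2.1 and SAP 7.7 make the fourth secondary endpoint a descriptive comparison of predose and EOI concentrations by arm and study day, with graphs of geometric means. Neither mentions draw lead or infusion length. A population PK model is optional and would be reported separately (Protocol 10.3.2.2, SAP 7.7).

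**The concern.** A sample taken before the infusion stops misses the drug not yet delivered. A fixed number of minutes is a larger part of a 30-minute infusion than of a 60-minute one. For ipilimumab, the sampling rule therefore lowers the EOI reading more in Arm B than in Arm A, and FRC looks higher even if the two methods deliver identical exposure.

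Ipilimumab EOI is one of the four quantities compared (predose and EOI, for each of two drugs). A reader of the graph could take the offset for a property of the formulation. Under slow loss during infusion the rule can even reverse the direction of a small true difference. Nivolumab runs over 60 minutes in both arms, so equal leads do not distort its EOI. Predose samples are not affected.

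**Working it through.** The documents give no figure for this effect, so there is none to reproduce.

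**Inputs from the documents.** Infusion length T is 60 minutes (Arm A) or 30 minutes (Arm B). The ipilimumab dose is 1 mg/kg in both. The lead t before the end is preferably 2-5 minutes.

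**Assumptions for the base case.** Constant rate, the same kinetics and the same lead in both arms, no predose level (Cycle 1), and no loss during infusion. The reading is then proportional to the share delivered, (T - t)/T.

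**Ratio A/B** = [(60 - t)/60] / [(30 - t)/30]

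| Lead t (min) | Arm A share | Arm B share | Ratio A/B |
|---|---|---|---|
| 0 | 1.0000 | 1.0000 | 1.000 |
| 2 | 0.9667 | 0.9333 | 1.036 |
| 3.5 | 0.9417 | 0.8833 | 1.066 |
| 5 | 0.9167 | 0.8333 | 1.100 |
| 6 | 0.9000 | 0.8000 | 1.125 |

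The undelivered share at 2-5 minutes is 3.3-8.3% in Arm A and 6.7-16.7% in Arm B.

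**Spread of leads.** If leads are uniform and alike in the two arms, the geometric mean ratio is 1.066 over 2-5 minutes and 1.047 over 0-5 minutes.

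**Unequal leads.** With 5 minutes in A and 2 in B, 0.9167/0.9333 = 0.982. With 2 in A and 5 in B, 0.9667/0.8333 = 1.160. The 0-5 minute extremes are 0.9167/1 = 0.917 and 1/0.8333 = 1.200. The lead is only a preference, so 0-10% is not a bound.

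**Loss during infusion.** With mono-exponential loss, the reading is proportional to (1 - exp(-k(T - t)))/(kT), where k = ln 2 / half-life. The documents give no early half-life for ipilimumab, so these are assumed:

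| Assumed half-life | t = 0 | t = 2 | t = 5 |
|---|---|---|---|
| 12 h | 0.986 | 1.021 | 1.084 |
| 24 h | 0.993 | 1.028 | 1.092 |
| 48 h | 0.996 | 1.032 | 1.096 |

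The true end-of-infusion ratio is slightly below 1 while the sampled ratio is above 1. An extreme 6 h half-life leaves an excess of 0.7% at 2 minutes and 6.9% at 5.

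**Later cycles.** With a predose level r, as a share of the full-dose increment, the ratio is (r + A share)/(r + B share). For assumed r = 0.2, 0.4 and 0.6 it is 1.029, 1.025 and 1.022 at 2 minutes, and 1.081, 1.068 and 1.058 at 5.

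**Against sampling noise.** With 50 per arm, the 95% limits on a geometric mean ratio are a factor of exp(1.984 × sqrt(ln(1 + CV²)) × sqrt(2/50)). This is 1.082, 1.124 and 1.165 for an assumed CV of 20%, 30% and 40%.

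**Does rescaling repair it?** Multiplying the increment over predose by D/(D - t), with D the infusion duration, divides the Cycle 1 ratios by 1.036 (t = 2) or 1.100 (t = 5). With no loss this returns 1.000. With loss it returns 0.986, 0.993 and 0.996, the true end-of-infusion ratios.

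**The case against.** The strongest reply is that nothing turns on this. SAP 7.1 rules out formal testing and p-values, and no PK margin is stated. One analyte at three visits is touched, and a typical 4-7% is inside a noise factor of 1.08-1.17. A shortfall in delivered FRC dose should still show in troughs and nivolumab EOI. All of that stands and is why the point ranks low.

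The figure is also conditional. Protocol 7.1.3 gives the infusion times as approximate; a 35-minute Arm B infusion would cut the 2-minute ratio to (58/60)/(33/35) = 1.025. No draw-time data are visible, so equal lead distributions in the two arms are an assumption. This stands too.

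Some handling exists. The rule for late-ending infusions moves the sample but keeps it before the end, so the bias remains. SAP 7.4.2.2 already tabulates interruptions and rate reductions by arm, so little new counting is needed. The population PK model could allow for the lead but may never be run.

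Unseen documents limit certainty: "Further details of sample collection, processing, and shipment will be provided in the laboratory procedures manual". The pharmacy documents may also settle how the line flush is handled and what counts as the stop time.

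Finally, rescaling is sensitive to recorded times. If a true lead of 2 minutes is recorded as 4 in both arms, Arm B is inflated by (28/30)(30/26) - 1 = 7.7% and Arm A by (58/60)(60/56) - 1 = 3.6%. That is a spurious 4% in the other direction. Rescaling therefore belongs in a sensitivity table and should not replace the main summary.

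**Conclusion.** The concern holds. Followed as written, the plan builds an arm-dependent bias into the ipilimumab EOI comparison, with FRC reading high. At Cycle 1 it is 3.6% at a 2-minute lead, 6.6% at 3.5 and 10.0% at 5, given equal leads, constant rate, identical kinetics and negligible loss. It is smaller at Cycles 2 and 4: 2.2-2.9% at 2 minutes and 5.8-8.1% at 5, under the assumed carry-over. It recurs at every EOI visit and more participants would not reduce it. It changes no test and does not touch the primary endpoint. This is a minor improvement worth considering.

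**What to change.** **Sampling rule.** In both arms, draw EOI samples at the end of drug delivery, or the same stated number of minutes after it, and record actual draw times. Arm B nivolumab must be drawn before ipilimumab starts. Define the end of delivery the same way in both arms with respect to the line flush. For Arm B the protocol states "The nivolumab infusion must be promptly followed by a saline flush to clear the line of nivolumab before starting the next infusion" and, for ipilimumab, "At the end of the infusion, flush the line with a sufficient quantity of normal saline or 5% dextrose solution". Its BMS-986237 paragraphs in 7.1.3 state no flush and refer to pharmacy documents, so the definition has to be explicit. Bring the nominal times in Table 9.5-1 into line with it.

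**Samples drawn under the current rule.** Where draw times exist, add a sensitivity table to SAP 7.7: scaled EOI = predose + (EOI - predose) × D/(D - t), with D the actual infusion duration and t the minutes before the actual stop. Exclude or flag interrupted or rate-changed infusions and give their number by arm. The formula assumes a constant rate, and the restart text in Protocol 7.4.5 differs by arm: for Arm B, "if no further complications ensue after 30 minutes, the rate may be increased to 100% of the original infusion rate", while for Arm A it names 50%. State that drug held up in the line is not corrected. Where draw times are missing, put a note on the arm-dependent bias beside the ipilimumab EOI table.

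**Cost.** A wording amendment with IRB/IEC review, one line in the laboratory manual, and one table or footnote. No samples are added. SAP Table 7.4.1-1 already uses infusion start and stop times, and Protocol 9.5 says "If the infusion was interrupted, the interruption details will also be documented on the CRF". The drawback is two sampling regimes within one study, which need a flag. If Part 1 sampling is largely complete, the table or footnote alone is the proportionate step.
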